6.1 Study examinations

The study examinations will be organized in modules.

All substances, methods, and medical products used in the study are approved for the use in humans and will be used according to approval.

Module 1: Medical history (questionnaire) and clinical basic testing (mandatory)

Included will be known diseases, blood glucose control, present diabetic complications, medication, allergies, size, weight, and hip/waist-ratio.

Module 2: Blood and urine testing (mandatory)

- **Basic laboratory testing**

- Total blood count (Leucocytes, red blood cells, platelets, hemoglobin, hematocrit, median corpuscular hemoglobin [MCH], median corpuscular volume [MCV], median corpuscular hemoglobin concentration [MCHC])
- Clinical chemistry: Sodium, potassium, calcium, magnesium, phosphate, triglycerides, total cholesterol, LDL-cholesterol, HDL-cholesterol, Lp(a), creatinine,

suPAR, calculated GFR, GOT/AST, GPT/ALT, GGT, AP, cholinesterase, hsCRP, total bilirubin, BUN, uric acid, ferritin, transferrin, transferrin saturation, iron (Fe), total protein, albumin

- Urine analysis: urine status, albumin, protein
- **Hormones, diabetes, glucose**
 - Fasting glucose, HbA1c, TSH, Parathormon
- **Samples for biobank**
 - Plasma for metabolomics/biomarkers
Collection of different stabilized plasma samples (Li-heparin, EDTA plasma, PBMC isolation, whole blood, citrate blood, serum, urine) at a fasting state for basic characterization, as well as EDTA plasma during interventional examinations (oGTT, clamp) to analyze different biomarkers, which are linked to the development of late diabetic complications. Collected material will be stored for up to 5 years and eliminated afterwards in case it was not needed for analyses.

With the participation in the clamp study, necessary total blood volume is 270 ml.

Module 3: insulin resistance module and asprosin cinetics

- **Euglycemic hyperinsulinemic clamp study**

It is a standard scientific test for the determination tissue sensitivity to insulin. In this study the asprosin kinetic in various hyperglycemic and euglycemic phases as well as the correlation between asprosin levels to the other known regulating hormones (adrenaline, norepinephrine, glucagon and cortisone) will be investigated. During the hyperglycemic phase, as well as at the end of the clamp test, the mechanical pain sensitivity (MPS) and the mechanical allodynia in the case of moving stimuli (DMA) are performed on both sides of the hands and feet. This in order to determine the changes in the sensibility of the skin, the sense of pain itself and sensitivity deficits with QST in the various hyperglycemic and euglycemic phases. The implementation of the QST is described in detail in page 15 of the study protocol.

The Examination-Clamp Test starts in the morning at 07:15 after a fasting period of 12 hours. Initially blood is drawn to determine plasma glucose, insulin, C-peptide, adrenaline, nor-

adrenaline, glucagon and cortisone levels. In order to construct the biobank and for the routine lab testing, blood tests are executed both at the beginning and end of the test. In addition, urine examination is also performed.

An intravenous glucose tolerance test (ivGTT) takes place, in which 1 ml / kg of glucose 30% is as bolus injected and the serum glucose is controlled over 1 hour, initially every 2 minutes and later in gradually prolonged intervals. Additionally blood tests for insulin, C-peptide and asprosin determination are executed. This test will be used to determine the pancreatic insulin reserve and to monitor asprosin kinetics during hyperglycemia.

Afterwards a glucose (20%) and an insulin solution (normal insulin 1.5 mU / kg body weight) is infused via an intravenous- cannula to the right elbow in order to set serum glucose manually at a target value of 90 mg / dl for a total duration of 1 hour. During this hour blood tests for the above mentioned hormones are performed. The same test is again performed with a glucose serum level of about 60 -70 mg / dl, corresponding to physiological fasting serum glucose values after prolonged fasting periods. This is done in order to be able to assess asprosin kinetics even at lower serum glucose levels. At the end of this last hour, blood tests for the measurement of serum insulin, C-peptide, asprosin, adrenaline, noradrenaline, glucagon and cortisone concentrations is performed. Including about two hours of follow-up after intravenous administration of Actrapid, the total duration of the examination is approximately 5 hours.

Indirect calorimetry (optional)

Measurement of O₂-uptake/CO₂-emission in a resting state and starving at the beginning, and again at the end of the clamp test for determination of substrate oxidation (glucose oxidation - GOX, lipid oxidation - LOX) in a resting state and with combined insulin and glucose infusion (Cosmed Quark RMR, Cosmed Deutschland GmbH, Fridolfing).

FibroScan® measurement (optional):

This is a pain-free, non.invasive clinical routine test of liver tissue using elastography (Echosens FibroScan®, Paris, Echosens™, Frankreich) for determination of liver stiffness, which can be used for steatosis follow up.

AGE measurement (mandatory):

Non.invasive fluorescence-based measurement of advanced glycation endproducts in the skin (DiagnOptics AGE Reader[®] SU, Diagnostics Technologies B.V., Groningen, Niederlande). No risks or contraindications are known for this method.

BIA measurement (not in patients with ICD or pacemaker):

Measurement of body components using bioelectrical impedance method (MEDI CAL Biacorus[®] RX 4000, MEDI CAL HealthCare GmbH, Karlsruhe). Sticky electrodes are attached to the patient's skin, resulting in minimal electric current. This method is widely used in clinical routine. For safety reasons, it is not used in patients with ICD or pacemaker. Other than that, no risks are known for this method.

Module 4: neuropathy module (optional)

- **NSS/NDS/SAS scores**

History of neuropathic symptoms using NSS and SAS scores, clinical detection by clinical-neurological testing using NDS score (monofilament, reflexes, cold-warm-discrimination, tuning fork).

- **Quantitative sensory testing and electrophysiological measurements**

Quantitative sensory testing (QST) is performed according to the protocol of the Deutscher Forschungsverbund Neuropathischer Schmerz (DFNS) (Rolke et al. 2006) for evaluation of subjective detection thresholds of sensory stimulation that allow to specifically test thick myelinated afferent fibers (low-threshold mechanic receptors for touch sensitivity and vibration), thin myelinated afferent fibers (cold detection, mechanical nociception), and non-myelinated afferent fibers (warm detection, heat-sensitive polymodal nociceptors). Testing includes thermal detection thresholds for cold and warm detection as well as paradox heat sensation, mechanical thresholds for touch sensitivity, vibration detection, and mechanical pain threshold (thresholds for bland pressure and needle-stings, dynamic allodynia, and summation of pain sensation in repeated stimuli).

Thermal detection, thermal pain thresholds

Measurement tool is a thermal sensory testing device (thermode). A standard test sequence is performed using a Thermal Sensory Analyzer (TSA by MEDOC, Israel). This

method is widely used in clinical research to detect the function of pain and thermal sensory fibers (C- and A-delta fibers) and has a CA-certification (TSA: CE 0473; MSA: CE 0413). Cold and warm detection thresholds are determined by this tool, as well as the thermal sensory limen (TSL) to detect paradox heat sensations (Fruhstorfer, Lindblom et al. 1976, Yarnitsky, Sprecher et al. 1995). Moreover, thermal pain thresholds can be tested using this thermode. For aforementioned testing, the thermode is applied to different areas (affected and non-affected) of the patient's skin. All thresholds are obtained by continuous up and down temperature stimuli (1°C/s) that are terminated when the study participant presses a stop-button. Cut-off temperatures are 0 und 50°C, with a baseline temperature at the beginning of all measurements of 32 °C. Contact area of the thermode is app. 13 cm². For thermal detection and pain thresholds, the mean value of a series of three measurements is used.

Determination of mechanical detection threshold

Measurement tool is a standardized set of modified von Frey hairs (0,25, 0.5, 1, 2, 4, 8, 16, 32, 64, 128, 256 und 512 mN). The contact area of the von Frey hairs with the skin is of uniform size (<1 mm²) and shape (rounded tip to avoid sharp edges that would facilitate nociceptor activation). Nominated von Frey hairs (Optihair) are available by Marstock Co. (Marburg) and CE certified (CE, Class 1, 1999 granted). Mechanical thresholds are determined according to the method of limits using a series of calibrated von Frey hairs in five series of ascending and descending forces of application at affected and non-affected areas of the skin. Beginning with a force of application of 16 mN, von Frey hairs are applied in decreasing order until the patient does not perceive the stimulus anymore, which represents the mechanical detection threshold. Afterwards, von Frey hairs are applied in reverse order until the stimulus is detected by the study participant, which represents the second value of mechanical detection threshold. This process is repeated five times. In case the first force of application of 16 nM is not perceived, von Frey hairs with ascending forces of application are used until the stimulus is perceived, which then represents the first threshold value. Afterwards, von Frey hairs are applied with decreasing forces of application until the study participant does not perceive the stimulus (second value). These steps are repeated five times.

Determination of mechanical pain threshold

Mechanical pain threshold is measured using a set of seven metallic punctual mechanical stimulators (Pin Pricks) with standardized force of application (8, 16, 32, 64, 128, 256 und 512 mN), which have a cylindrical tip as contact area to the skin with no risk of skin injuries by appropriate use. Pin Pricks are used according to the method of limits, with the threshold being the geometric mean of five series of ascending and descending forces of application on affected and non-affected skin areas (Hampf, Bowsher et al. 1990, Ziegler, Piolot et al. 1999). The investigator uses Pin Pricks with different forces of application to detect the mechanical pain threshold. Only the needle itself and not the syringe barrel should be brought in to contact with the skin of the subject. The application and removal should be performed by a gentle movement leading to an application duration of 2 seconds. Beginning with the force of 8 mN, the stimuli are subsequently applied in increasing order of the intensity until the perception of the skin-contact is altered with an additional sharp sensation, at which point the applied force represents the first threshold value. Afterwards, Pin Pricks are used in reverse order (meaning descending forces of application) until the study participant perceives the stimulus without sharp sensation (second value). This procedure is repeated five times.

Determination of the mechanical pain sensitivity and dynamic mechanical allodynia for stroking stimuli/touch

Mechanical pain sensitivity is tested using the same set of Pin Pricks as used for mechanical pain threshold with the intensities of 8, 16, 32, 64, 128, 256 und 512 mN. An additional set of three light tactile stimulators including a cotton wisp exerting with a force of application of approximately 3 mN, a Q-tip (fixed to an elastic strip) exerting a force of application of approximately 100 mN, as well as a standardized brush (Somedic, Sweden) exerting a force of 200-400 mN is used for this testing (Rolke, Baron et al. 2006, Rolke, Magerl et al. 2006). These stimuli are applied in a fixed, balanced order for both affected and non-affected parts of the skin. This stimulus-response-function test is able to detect hyper- and hypoalgesia, as well as mechanical allodynia (Ziegler, Piolot et al. 1999). The Pin Pricks are applied as described above, whereas the tactile stimulators are applied with a single stroke (1-2 cm in length) over the skin. The study participant should give a pain rating for each stimulus on a verbal numerical rating scale (1-100). "0"

indicating “no pain” or “touch only”. The not-perceived stimuli should label ‘Ø’. “100” is indicating the most intense pain imaginable. Before the procedure, the finest and the most intense Pin Pricks as well as the cotton wisp, Q-tip and brush are demonstrated on the study participant on an exercise area.

Wind-up ratio

Measurement tool is a mechanical stimulator with standardized intensity (256 mN Pin Prick), which has a flat contact area (diameter 0.2 mm). Firstly, a single stimulus is applied with the 256 mN Pin Prick as described above, with the study participant rating the pain on a scale from 0-100 as described above. At intervals of 10 sec., trains of ten stimuli of the same force are applied repeatedly at a rate of 1/sec. within a small skin area of 1 cm². Directly after the subsequent train of stimuli, the study participant rates the pain again on the scale from 0-100. Out of the main pain rating of trains and the main pain rating of single stimuli, a quotient is calculated. This procedure is repeated five times. The wind-up ratio is calculated as the geometric mean of all five quotients (Magerl, Wilk et al. 1998). Before starting the actual procedure, it should be demonstrated on an exercise area.

Vibration detection threshold

Measurement tool is a tuning fork (64 Hz, 8/8 scale) as used in a clinical routine. To examine the vibration threshold, the tuning fork is placed on a bony prominence of a test- and control site (for example: on the feet on medial malleolus, on hands on processus styloideus ulnae, on head lateral on temples). Vibration threshold is determined by a series of three descending stimulus intensities (Fagiuz and Wahren 1981).

Detection of pressure pain threshold over skeletal muscles

Measurement tool is a bland mechanical stimulator with a contact area 1 cm², and an applied force of up to 20 kg/ 2000 kPa/ 200 N (or 10 kg/ 1000 kPa/ 100N when applied on the face), which has a scale for measurement of applied pressure (for example pressure algometer, Wagner Instruments, Greenwich, USA). This stimulator is applied to

an affected and an unaffected area of the skin over defined skeletal muscle areas (for example on the feet over the abductor hallucis muscle, or on the thenar of the hands, or over temporal muscle in the face). By applying constantly increasing pressure at a rate of 0.5 kg/sec. or 50 kPa/sec., pressure pain threshold of respectively tested will be defined.

Study participants who show signs of significant central nervous sensitization due to their QST profile will be asked to participate in further testing performed at the Neurophysiological institute (Director: [name]). There is an extra statement by the Ethics committee of the University of Mannheim for this additional testing, where it will be performed, so that they do not concern the University of Heidelberg.

Axonal excitability. One important parameter of planned testing is the excitability of axonal membranes of myelinated peripheral nerve fibers. For that, the method of “threshold tracking” will be performed, where the current will be analyzed via computer that is necessary for induction of an A-fiber summation potential with 40% of the largest possible amplitude (100%). Increase or decrease of this current due to simultaneous subliminal pre-depolarization shows an increase or an inhibition of excitability, respectively. The method of “threshold tracking” and the software needed (QTRAC; © [name], University London) have been established by our cooperation partners in Mannheim for several years (Fleckenstein et al, 2013). In addition to excitability, recovery phase of membrane threshold after an action potential of myelinated nerve fibers will be registered. For this, threshold of the current necessary for triggering a second action potential after a conditioning first action potential will be analyzed. Time gap between these two is variable between 10 and 400 msec. This recovery phase after an action potential is an indirect parameter for the membrane potential of myelinated nerve fibers. Main parameter is a change in relative refractory time of the recovery cycle. Changes in strength-duration time constant, rheobase current, refractoriness after 2 msec., superexcitability after 7 msec., as well as changes in threshold electrotonus.

Axonal excitability is measured by threshold tracking technique (Bostock et al, 1998) with the help of an multiple excitability measures (MEM) protocol (Kiernan et al, 2000), which is an automatic computer-based electric stimulation protocol (QTRAC Software, Institute of Neurology, London, UK). This protocol consists of a standardized sequence of electric

pulses, which are powerful enough to trigger A-fibers, but are still sub-threshold for thin C-fibers. Such evoked sensations are not painful, but are often felt as electrifying or tingling. Measurements are performed under supervision by a medical doctor and take about 10-15 minutes per site. Axonal excitability of motoric A-fibers is measured according to changes in summing potential of the abductor pollicis brevis muscle. Electrodes are placed over median nerve on the lower arm. Excitability measurements of sensory A-fibers are evoked by electrodes placed over either the median nerve, or the ulnar nerve on the wrist. Ring electrodes are used as lead electrodes, and will be placed on the base of the middle- or ring-finger.

For electric stimulation, a CE-certified (EN(IEC) 60601) constant current stimulation device (DS5 Digitimer) will be used. This device has a protection circuit, which only allows a defined maximum energy to be used for stimulation, independently of computer or user mistakes. For detection, a CE-certified (ICE 60601-1, 2000) AC-coupled EMG-amplifier (LP511, Grass Technologies) will be used. The power supply of this amplifier is medically regulated and uses DC voltage of ± 12 V.

Moreover, the same stimulation device will be used for determination of the sensitivity of skin nociceptors to depolarization. For this, sinus-wave-form electric stimuli with a duration of 0.5 sec. Will be applied to the skin by bipolar platinum-iridium stick electrodes (0,4 mm diameter, 1 cm length, 3 mm distance; Cephalon, Maastricht, Niederlande). Maximum current randomly varies between 0.2 and 0.8 mA, and will be repeated three times. After every stimulus, study participants will be asked to give a pain rating on a scale from 0-10, with 0 being „no pain“ and 10 being „the strongest imaginable pain“. Currents used are so weak (max. 0.8 mA) that no damage to the skin will occur. Expected maximum pain in healthy persons is around 3 out of 10. Study participants with diabetic polyneuropathy will usually feel less pain.

- **Heart rate variability:**

Determination of heart rate variability as surrogate parameter for autonomic neuropathy (SUESS SUEmpathy[®] 100, SUESS Medizin-Technik GmbH, Aue). For this, a normal 3-lead ECG will be used, so that this method is completely non-invasive.

- **Measurement of nerve conduction velocity of sural nerve, peroneal nerve, and tibial nerve:**

By use of sticky electrodes, minimal electric current will be applied, which is only felt as tingling by the study participants (Viasys Healthcare VikingQuest[®], Viasys Healthcare GmbH, Höchberg). This examination will not be performed in persons with ICD or implanted pacemaker devices. Otherwise it is free of risks and frequently used in clinical routine.

Module 5: Vascular module (mandatory)

- **Physical examination**

Palpation of the following pulses on both legs: Femoral artery, popliteal artery, dorsal pedic artery, posterior tibial artery. Non-invasive measurement of blood pressure by Riva-Rocci method, and pulse by palpation.

- **Intima-Media-thickness (IMT) of carotid artery**

Determination of IMT by use of high-resolution ultrasound technique (Samsung SonoACE[®] X8, Samsung Medison Co. Ltd.) as important surrogate parameter for vascular complications. For measurement, internationally accepted protocols are used.

- **Doppler ultrasound of carotid artery**

By use of ultrasound (Samsung SonoACE[®] X8, Samsung Medison Co. Ltd.), blood flow velocity of carotid artery will be examined in order to detect plaque or stenoses. Stenoses will be classified according to NASCET-criteria.

- **Abdominal ultrasound**

Abdominal ultrasound (Samsung SonoACE[®] X8, Samsung Medison Co. Ltd.) by use of a 3.5 MHz probe will be performed with focus on the following parameters: Size and morphology of the kidneys, perfusion of the kidneys, diameter of the infrarenal abdominal aorta, and liver parenchyma (NAFLD).

- **12-lead ECG**

Key parameters are cardiac rhythm, indication for coronary artery disease or former myocardial infarction (Mortara Instrument ELI250, Mortara Instrument GmbH, Essen).

- **Ankle-brachial-index (ABI-Messung):**

Non-invasive blood pressure measurement on arms and legs by use of Riva-Rocci method (BOSO ABI-System 100, Bosch + Sohn GmbH, Jungingen). This examination will not be performed on study participants with lymphedemas or after lymphadenectomy. Otherwise it is free of risks without further known contraindications.

- **Fundus photography**

Capturing retinal pathologies by use of central 1-field-photography (NIDEK AFC-230[®], NIDEK CO LTD, Padova, Italien; Canon EOS 5D Mark II, Canon Deutschland GmbH, Krefeld). For this method, no mydriasis is necessary, so that no eye drops will have to be used, and no direct contact to the eye will be necessary. Therefore, this method is free of risks, non-invasive, and widely used in clinical routine.

Module 6: Pulmonary examination (mandatory in case of no contraindications)

- Clinical auscultation of the lung with a stethoscope.

- **Lung function testing**

Lung function testing will be performed by bodyplethysmography (Ganshorn PowerCube[®] Body+ und Diffusion+, Ganshorn, Niederlauer). This is a non-invasive clinical routine method. It is not performed in case instructions are not understood by the study participant, or if the study participant exceeds a body weight of 160 kg since this is the maximum weight for which the cabin is approved.

- **Pulsoxymetry**

Non-invasive measurement of oxygen saturation by use of a finger clip (Pulox[®] PO-250, Novodion GmbH, Köln).

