6.3 Selection of study participants

Inclusion criteria for participants without hypoglycemia unawareness

- Age between ≥ 18 and ≤ 75 years
- BMI between 20 und 35 kg/m²
- Persons with manifest diabetes mellitus type 1 and diagnosis according to DDG guidelines 2011 oGTT, HbA1c $\geq 6.5\%$ in the absence of adulteration of the HbA1c, over 200 mg / dl in the 2 hour value of the oGTT, fasting glucose > 126 mg/dl, spontaneous glucose > 200 mg/dl at least twice).

Inclusion criteria for participants without hypoglycemia unawareness

- Persons who are not aware of hypoglycemia symptoms at glucose levels above 50 mg / dl
- Age between ≥ 18 and ≤ 75 years
- BMI between 20 und 35 kg/m²
- Persons with manifest diabetes mellitus type 1 and diagnosis according to DDG guidelines 2011 oGTT, HbA1c $\geq 6.5\%$ in the absence of adulteration of the HbA1c, over 200 mg / dl in the 2 hour value of the oGTT, fasting glucose > 126 mg/dl, spontaneous glucose > 200 mg/dl at least twice).

General exclusion criteria

- Secondary types of diabetes (ADA-criteria type 3 B-H)
- Current pregnancy
- Acute infections / fever
- Immune-suppressant therapy
- Severe psychiatric diseases requiring treatment (for example personality disorders, schizophrenia, depression)
- Known alcohol or drug dependency
- Severe heart-, kidney-, or liver-insufficiency:
 - NYHA stadium IV
 - Non-diabetic liver disease (for example PBC, PSC, Wilson's disease, hemochromatosis, autoimmune hepatitis)

- severe peripheral artery disease (stadium IV)
- non-diabetic glomerulopathy
- Cancer or other malignant diseases within the last 5 years
- Infectious diseases like hepatitis B, C, E, or HIV
- Other severe autoimmune diseases
- Current participation in an interventional study
- Anemia or disorders of bone marrow
- **Exclusion criteria for clamp study:**
 - Past history of deep vein thrombosis or pulmonary embolism
 - Routine laboratory test results $\leq 80\%$ below lower reference value: Ferritin, iron, leucocytes, haemoglobin, hematocrit, RBC, platelets, blood alcohol levels.
- **Exclusion criteria for bioimpedance measurement:**
 - Pacemaker / ICD
- **Exclusion criteria for lung function testing:**
 - Ignoring or non-understanding of the instructions

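### Blood alcohol bars a person from the clamp as a routine laboratory result, but no scheduled test names it and the cut-off attached to it points the wrong way

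*Protocol*

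**What the plan says.** Protocol section 6.3 has a separate list of exclusions for the clamp. One entry refers to routine laboratory results that fall short of the lower reference value, with 80% as the stated figure, and applies this to "Ferritin, iron, leucocytes, haemoglobin, hematocrit, RBC, platelets, blood alcohol levels".

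The routine laboratory work is set out in section 6.1, Module 2, which is mandatory. Its blood count begins "Total blood count (Leucocytes, red blood cells, platelets, hemoglobin, hematocrit" and continues to the red cell indices. Its chemistry list ends "ferritin, transferrin, transferrin saturation, iron (Fe), total protein, albumin". The hormone, diabetes and glucose line is "Fasting glucose, HbA1c, TSH, Parathormon", and the urine line is "Urine analysis: urine status, albumin, protein".

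For the clamp day, the introduction to section 6, Module 3 in section 6.1, and section 6.4 name glucose, asprosin, insulin, C-peptide, adrenaline, noradrenaline, glucagon and cortisone. All three also schedule routine laboratory work and a urine examination without saying what these contain.

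Among the general exclusions, section 6.3 lists "Current pregnancy". The age criterion is "Age between ≥ 18 and ≤ 75 years", and no restriction by sex is stated. The history in Module 1 is described as follows: "Included will be known diseases, blood glucose control, present diabetic complications, medication, allergies, size, weight, and hip/waist-ratio".

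**The concern.** An exclusion that depends on a laboratory value works only if the value is measured and the cut-off selects the people it is meant to select. For blood alcohol, the itemised plan secures neither. A site that follows Module 2 and the named clamp-day analytes to the letter would have no alcohol result. A site that did have one would find a rule aimed at low values.

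The procedure behind this exclusion is the one in Module 3, where insulin is infused and glucose is brought to 60–70 mg/dl for an hour. Half of the ten participants are to have hypoglycemia unawareness, and section 6.5 accepts that hypoglycemia can occur during or shortly after the clamp. What is at stake is whether an exclusion the protocol itself chose is applied. With five people per subgroup, one person who should have been excluded is 1/5 = 20% of that subgroup.

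**Working it through.** The plan gives no figure to reproduce, so the check sets the passages side by side.

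**Step 1. Clamp exclusions (section 6.3) against the itemised panel (section 6.1, Module 2).**

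| Section 6.3 item | Where it is in Module 2 |
|---|---|
| Ferritin | Clinical chemistry |
| Iron | Clinical chemistry |
| Leucocytes | Blood count |
| Haemoglobin | Blood count |
| Hematocrit | Blood count |
| Red blood cells | Blood count |
| Platelets | Blood count |
| Blood alcohol | Not named |

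Named: 7 of 8. Not named: 8 − 7 = 1.

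**Step 2. Clamp-day draws.** The analytes named in the section 6 introduction, Module 3 and section 6.4 are glucose, asprosin and the hormones listed above. Alcohol is not among them. The routine work on that day is not itemised, so it may or may not include alcohol. The only description of a routine panel in the documents is Module 2, which does not.

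**Step 3. Direction of the cut-off.** Let L be the lower reference value of an analyte and x the result. Read as 80% of the lower limit, the rule excludes when x ≤ 0.8 × L. This makes sense for the other seven, where a low value is the problem. For alcohol, any x above 0.8 × L passes, however high it is, and this holds for every L. The documents give no reference range for alcohol. If L is assumed to be 0, the cut-off is 0.8 × 0 = 0, so a person with no alcohol would meet the exclusion and a person with a measurable level would not. Any other reading of the 80% phrase still selects low values, because it is framed as a shortfall.

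**Step 4. Timing.** The clamp takes place within four weeks of basic testing (section 6 introduction and section 6.4). An alcohol value from the basic testing day would not describe the clamp day, so naming the assay in Module 2 without a time would not be enough.

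**Step 5. Pregnancy.** Module 1 names neither pregnancy nor alcohol intake. Module 2 names no pregnancy test in blood or urine. Pregnancy tests named in any scheduled work: 0. Unlike blood alcohol, however, section 6.3 does not describe pregnancy as a laboratory result.

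**The case against.** The best defence is that the clamp-day routine laboratory work is left open. Section 6.3 itself classes blood alcohol as routine, and the protocol refers to SOPs that are not among the documents. Alcohol may well be measured in practice. This stands as far as it goes: a reader might infer that the alcohol exclusion cannot be applied at all, and the documents do not support that. They support only that no test for it is named. The defence does not touch the direction of the cut-off, which would make a measured value unusable as written.

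A second defence concerns pregnancy. The general exclusions are plainly not all meant to be read off the panel: hepatitis B, C and E, HIV and drug dependency are also excluded, and Module 2 names no test for them. A study doctor sees each person at a separate consent appointment and can ask, and the consent pages are not available for review. This largely stands. A reader might infer a second contradiction of equal weight, but the protocol never ties pregnancy to a laboratory result. What remains is that no method is named, and that asking cannot find an unrecognised pregnancy.

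Third, the effect on the results is limited. It is tempting to say that one ineligible person could distort a subgroup. In a group of five, changing one value moves the median at most to a neighbouring ordered value, and the SAP uses medians and non-parametric tests. It also reports the range, which a single value can set, but nothing in the documents says how alcohol would move asprosin. The case for a change therefore rests on applying the protocol's own exclusion, not on bias.

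**Conclusion.** The point holds for blood alcohol as an internal inconsistency with two parts. One of the eight laboratory exclusions for the clamp is missing from the itemised panel and from every named clamp-day draw, and its cut-off is worded for low values. Either part alone would leave the exclusion unreliable, and adding the assay without rewording the criterion would not repair it. For pregnancy the point is secondary: an exclusion without a stated means of ascertainment, and not a contradiction.

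This rests on two assumptions: that Module 2 is the routine panel section 6.3 has in mind, and that the exclusion is meant to catch raised alcohol levels. If an SOP already lists the assay, the first part becomes a matter of carrying it into the protocol. The second part remains.

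No sample size, test or estimate in the SAP changes. The number of participants affected cannot be estimated from the documents. The matter still deserves correction, because it concerns a safety exclusion before an insulin-driven low-glucose phase and costs little to put right.

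**What to change.** Reconcile section 6.1 (Modules 2 and 3) with section 6.3, and carry the result into section 6.4:

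- Name blood alcohol in the routine laboratory work done on the initial clamp-day blood, which is already drawn.
- Take alcohol out of the entry about values below the lower reference limit and give it its own line, so that the exclusion can be applied as intended. The threshold and the timing are for the sponsor to set.
- Say what the clamp-day routine laboratory work and urine examination contain, by listing the items or by reference to Module 2 or an SOP.
- Name how pregnancy is ascertained where applicable, for example by a test on the urine already collected on the clamp day. The documents expressly schedule urine only for that day. Module 2 also lists urine but is not assigned to a day, so a basic-testing sample should not be presumed.

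The cost is one assay and one urine test on samples already taken, plus a few lines of protocol text. No visit is added, and the statistical analysis is unchanged.
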